3.6.3.2 Mean change from baseline

Change from baseline in the following secondary PRO endpoint from EORTC QLQ C30 will be assessed:

- Global health status/QoL score (EORTC QLQ-C30)

The time point for the mean change from baseline analysis is defined as the latest time point at which CR-T $\geq 60\%$ and CR-E $\geq 80\%$ based on blinded data review prior to the database lock for any PRO analysis and will be documented in a future sSAP amendment.

To assess the treatment effects on the PRO score change from baseline outcomes, a

constrained longitudinal data analysis (cLDA) model proposed by Liang and Zeger [Ref. 5.4: 00QJ0M] will be applied, with the PRO score as the response variable, and treatment, time, the treatment by time interaction, and stratification factors used for randomization (see protocol Section 6.3.2) as covariates.

The treatment difference in terms of least square (LS) mean change from baseline will be estimated from this model together with 95% CI. Model-based LS mean with 95% CI will be provided by treatment group for PROscores at baseline and post-baseline time point.

The cLDA model assumes a common mean across treatment groups at baseline and a different mean for each treatment at each of the post-baseline time points. In this model, the response vector consists of baseline and the values observed at each post-baseline time point. Time is treated as a categorical variable so that no restriction is imposed on the trajectory of the means over time. The cLDA model is specified as follows:

$$E(Y_{ijt}) = \gamma_0 + \gamma_{jt} I(t > 0) + \beta X_{i,j} \quad i=1,2,3,\dots,n; t=0,1,2,3,\dots$$

where Y_{ijt} is the PRO score for participant i , with treatment assignment j at visit t ; γ_0 is the baseline mean for all treatment groups, γ_{jt} is the mean change from baseline for treatment group j at time t ; $X_{i,j}$ is the stratification factor (binary) vector for this participant, and β is the coefficient vector for stratification factors. An unstructured covariance matrix will be used to model the correlation among repeated measurements. If the unstructured covariance model fails to converge with the default algorithm, then Fisher scoring algorithm or other appropriate methods can be used to provide initial values of the covariance parameters. In the rare event that none of the above methods yield convergence, a structured covariance such as Toeplitz can be used to model the correlation among repeated measurements. In this case, the asymptotically unbiased sandwich variance estimator will be used. The cLDA model implicitly treats missing data as missing at random (MAR).

Line plots for the empirical mean change from baseline will be provided across all time points as a supportive analysis.

In addition, the model-based LS mean change from baseline to the specified post-baseline time point together with 95% CI will be plotted in bar charts.

3.6.3.3 Time to Traditional Deterioration (TTD)

The Kaplan-Meier method will be used to estimate the TTD curve for each treatment group. The estimate of median time to deterioration and its 95% confidence interval will be obtained from the Kaplan-Meier estimates. The treatment difference in TTD will be assessed by the stratified log-rank test. A stratified Cox proportional hazard model with Efron's method of tie handling and with a single treatment covariate will be used to assess the magnitude of the treatment difference (i.e, HR). The HR and its 95% CI will be reported. The same stratification factors used for randomization (see protocol Section 6.3.2) will be used as the stratification factors in both the stratified log-rank test and the stratified Cox model.

- Time to Traditional Deterioration (TTD) as measured by EORTC QLQ-C30 global health status/quality of life scores. TTD is defined as the time from baseline to the first onset of a 10 or more points deterioration from baseline with a subsequent visit of 10 or more points deterioration from baseline.

The approach for the TTD analysis will be based on the assumption of non-informative censoring. The participants who do not have deterioration on the last date of evaluation will be censored. [Table 6](#) provides censoring rule for TTD analysis.

Table 6 Censoring Rules for Time-to-Deterioration

Scenario	Outcome
Deterioration documented	Event observed at time of assessment (first deterioration)
Ongoing or discontinued from study without deterioration	Right censored at time of last assessment
No baseline assessments	Right censored at treatment start date

3.6.3.4 Analysis Strategy for Key PRO Endpoints

Table 7 Analysis Strategy for Key PRO Endpoints

Endpoint/Variable	Statistical Method	Analysis Population	Missing Data Approach
Mean change from baseline in EORTC QLQ-C30/QoL	cLDA model	FAS	Model-based. Table 1
TTD in EORTC QLQ-C30/QoL	stratified log-rank test and HR estimation using stratified Cox model with Efron's tie handling method	FAS	Censored according to rules in Table 6 .

3.6.4 Demographic and Baseline Characteristics

The comparability of the treatment groups for each relevant demographic and baseline characteristic will be assessed by the use of tables and/or graphs. No statistical hypothesis tests will be performed on these characteristics. The number and percentage of participants screened and randomized and the primary reasons for screening failure and discontinuation will be displayed. Demographic variables, baseline characteristics, primary and secondary diagnoses, and prior and concomitant therapies will be summarized by treatment either by descriptive statistics or categorical tables.

3.7 INTERIM AND FINAL ANALYSES

Blinding to treatment assignments will be maintained at all investigational sites. The results of interim analyses will not be shared with investigators prior to completion of the study. Participant-level unblinding will be restricted to an external unblinded statistician and scientific programmer performing the interim analysis, who will have no other responsibilities associated with the study.

An external DMC will serve as the primary reviewer of the results of interim efficacy and futility analyses and safety analyses, and will make recommendations for discontinuation of the study or protocol modifications to the study EOC. If the DMC recommends modifications to the design of the protocol or discontinuation of the study, the EOC (and potentially other limited Sponsor personnel) may be unblinded to results at the treatment level to act on these

recommendations. The extent to which individuals are unblinded with respect to results of interim analyses will be documented by the unblinded statistician. Additional logistical details will be provided in the DMC charter. Key aspects of the interim analyses are described below.

Treatment-level results from the interim analysis will be provided to the DMC by the unblinded statistician. The unblinded statistician will not be involved in any discussions regarding modifications to the protocol, statistical methods, identification of protocol deviations, or data validation efforts after the interim analyses.

Access to the allocation schedule for summaries or analyses for presentation to the eDMC will be restricted to an unblinded external statistician, and, as needed, an external scientific programmer performing the analysis, who will have no other responsibilities associated with the study.

If the study is positive at an interim analysis for either primary endpoint, additional analyses, including but not limited to the protocol-specified final analysis, may be carried out for exploratory purposes or upon regulatory request.

3.7.1 Efficacy and Futility Interim Analyses

Two interim efficacy analyses and two interim futility analysis are planned in addition to the final analysis for this study. For the interim and final analyses, all randomized participants will be included. Results of the interim analyses will be reviewed by the DMC. Details of the boundaries for establishing statistical significance with regard to efficacy are discussed further in Section 3.8.

The analyses planned, endpoints evaluated, and drivers of timing are summarized in [Table 8](#).

Table 8 Summary of Interim and Final Analysis Strategy

Analyses	Key Endpoints	Timing	Estimated Time after First Participant Randomized	Primary Purpose of Analysis
Futility Analysis 1	PFS ORR	~297 participants enrolled ≥151 PFS events	~16 months	
 Non-binding futility IA for PFS and ORR
Futility Analysis 2	PFS ORR	~370 participants enrolled ≥191 PFS events	~20 months	
 Non-binding futility IA for PFS and ORR
IA1	PFS OS ORR if both PFS and OS are rejected	≥530 PFS events ~386 OS events expected at this time	~24 months	
 Interim PFS and OS analyses Final ORR analysis
IA2	PFS OS	≥558 PFS events ~469 OS events	~30 months	
 Final PFS analysis Interim OS analysis
FA	OS	~552 OS events	~39 months	Final OS analysis

Abbreviations: FA = final analysis; IA = interim analysis; ORR = objective response rate; OS = overall survival; PFS = progression-free survival.

3.7.2 Safety Interim Analyses

The DMC will conduct regular safety monitoring. The safety data will be reviewed during a safety run-in after 40 participants have been enrolled and have received 2 Cycles of treatment. If the DMC notes any safety concerns, the protocol will be amended. It is estimated that this review will include approximately 15 participants and no less than 10 patients will have ECOG PS 2. If the initial review includes fewer than 10 participants with ECOG PS 2, an additional DMC review would be conducted after 15 participants with ECOG PS 2 have received 2 Cycles of treatment. The timing and interval of safety monitoring will be specified in the DMC charter.

[figure not shown]
3.8 MULTIPLICITY

The study uses the graphical method of Maurer and Bretz [Ref. 5.4: 045MYM] to control multiplicity for multiple hypotheses as well as interim analyses. According to this approach, study hypotheses may be tested more than once, and when a particular null hypothesis is rejected, the α allocated to that hypothesis can be reallocated to other hypothesis tests.

Figure 1 shows the initial 1-sided α allocation for each hypothesis in the ellipse representing the hypothesis. The weights for re-allocation from each hypothesis to the others are shown in the boxes on the lines connecting hypotheses.

Initial α assigned to OS and PFS will be 0.02 and 0.005, respectively. If either hypothesis is rejected, α will be reallocated to the other hypothesis. If both are rejected, the ORR hypothesis will be tested at 0.025 (Figure 1).

Abbreviations: ORR = objective response rate; OS = overall survival; PFS = progression-free survival.

Note: If both PFS and OS null hypotheses are rejected, the allocation strategy allows testing of ORR at $\alpha = 0.025$.

Figure 1 Multiplicity Diagram for Type I Error Control

3.8.1 Futility Analysis

After reviewing the safety data at the 3rd DMC safety meeting on August 7, 2020, the DMC requested that efficacy data be provided along with safety data at the 4th DMC safety review. The DMC made a similar request after the 4th DMC meeting. In order to provide a statistical framework for the DMC to evaluate benefit-risk, non-binding futility boundaries have been provided for ORR and PFS. The non-binding futility analyses on ORR and PFS will be performed at approximately 16 and 20 months from FPI, when approximately 297 and 370 participants have been enrolled and approximately 151 and 191 PFS events have been observed.

All participants randomized as of the last patient last visit for the futility analyses will be included in the comparisons of PFS between the 2 randomized treatment groups. An observed hazard ratio (combination / pembrolizumab monotherapy) greater than approximately 1.3 and 1.2 would be sufficient for the eDMC to consider futility at each analysis. The actual PFS boundaries will be determined by the actual number of PFS events

at the time of the analysis using the pre-specified Hwang-Shih-DeCani beta-spending function with gamma parameter (-9). [Table 9](#) shows the probability of stopping the study for futility under different scenarios.

Table 9 Futility Scenarios for PFS (Superiority in Progression Free Survival – Combo vs Pembrolizumab in All Subjects)

PFS Events	Approx. Observed HR at Boundary	Cumulative Probability (%) of Stopping for Futility Under:			
		HR = 1.3	HR = 1.2	Null HR = 1	Alternative HR = 0.7
151 (27% IF)	1.3	49.1	30.4	5.2	<1
191 (34% IF)	1.2	71.1	50.3	10.6	<1
HSD (-9) Spending function is used					

Approximately 252 and 335 participants who have available imaging responses from BICR per RECIST 1.1 will be used to compare the ORRs between the 2 randomized treatment groups in the two futility analyses. Approximate observed differences in the ORRs (combination – pembrolizumab monotherapy) less than -10% at the first futility analysis and less than -5% at the second futility analysis would be sufficient for the eDMC to consider futility. The actual ORR futility boundaries will be determined by the actual number of participants included in the ORR analysis using a Hwang-Shih-DeCani beta-spending function with gamma parameter (-10).

[Table 10](#) shows the probability of stopping the study for futility under different scenarios.

Table 10 Futility Scenarios for ORR (Superiority in Objective Responsive Rate – Combo vs Pembrolizumab in All Subjects with Imaging by BICR per RECIST 1.1)

Sample Size	Approx. Observed Δ ORR at Boundary	Cumulative Probability (%) of Stopping for Futility Under:			
		Δ ORR = -10%	Δ ORR = -5%	Null Δ ORR = 0	Alternative Δ ORR = 17%
252 (36% IF)	-10%	60.9	24.3	5.9	<1
335 (48% IF)	-5%	88.7	54.5	17.8	<1
HSD (-10) Spending function is used					

All of the available data (ORR, PFS, and safety) will be considered by the eDMC in their deliberations in considering whether to recommend stopping the study for futility.

3.8.2 Objective Response Rate

The study will test the ORR hypothesis at the interim analysis 1 (IA1), at an α level of 0.025 if both OS and PFS hypotheses are rejected.

Based on the 694 randomized participants with at least 3 months of follow-up, power at $\alpha=0.025$, as well as the approximate treatment difference required to reach the bound (Δ ORR), are shown in [Table 11](#), assuming underlying 30% and 47% response rates in the control and experimental groups, respectively.

If, at IA2, the OS test does not achieve statistical significance but the PFS test achieves statistical significance, the p-value of the ORR test from IA2 will be compared to 0.025 if the null hypothesis for OS is later rejected.

Table 11 Possible α Levels and Approximate Objective Response Rate Difference Required to Demonstrate Efficacy for Objective Response at Interim Analysis

α	$\sim\Delta$ Objective Response Rate (ORR)	Power (Δ ORR=0.17)
0.025	0.073	0.996

3.8.3 Progression-free Survival

The PFS hypothesis may be tested at $\alpha=0.005$ (initially allocated α) or $\alpha=0.025$ (if the OS null hypothesis is rejected). [Table 12](#) shows the bounds and boundary properties for PFS hypothesis testing derived using a Lan-DeMets O'Brien-Fleming spending function. If the actual number of PFS events at the interim and final analyses differs from those specified in the table, the bounds will be adjusted using the Lan-DeMets O'Brien-Fleming spending function accordingly.

Table 12 Efficacy Boundaries and Properties for Progression-free Survival Analyses

Analysis	Value	$\alpha=0.005$	$\alpha=0.025$
IA1:95%* N = 694 Events: 530 Month: 24	Z	2.654	2.025
	p (1-sided) ^a	0.004	0.021
	HR at bound ^b	0.794	0.839
	P(Cross) if HR=1 ^c	0.004	0.021
	P(Cross) if HR=0.7 ^d	0.927	0.981
Final: N = 694 Events: 558 Month: 30	Z	2.657	2.062
	p (1-sided) ^a	0.004	0.02
	HR at bound ^b	0.799	0.840
	P(Cross) if HR=1 ^c	0.005	0.025
	P(Cross) if HR=0.7 ^d	0.947	0.986

Abbreviations: HR = hazard ratio; IA = interim OS analysis (PFS final analysis).
The number of events and timings are estimated approximately.
*Percentage of the target number of events at final analysis anticipated at interim analysis
^a p (1-sided) is the nominal α for testing.
^bHR at bound is the approximate HR required to reach an efficacy bound.
^cP (Cross if HR=1) is the probability of crossing a bound under the null hypothesis.
^dP (Cross if HR=0.7) is the probability of crossing a bound under the alternative hypothesis.

3.8.4 Overall Survival

The OS hypothesis may be tested at $\alpha=0.02$ (initially allocated α) or $\alpha=0.025$ (if the PFS null hypothesis is rejected). [Table 13](#) shows the bounds and boundary properties for OS hypothesis testing derived using a Lan-DeMets O'Brien-Fleming spending function.

Table 13 Efficacy Boundaries and Properties for Overall Survival Analyses

Analysis	Value	$\alpha=0.02$	$\alpha=0.025$
IA1: 70%* N = 694 Events: 386 Month: 24	Z	2.549	2.439
	p (1-sided) ^a	0.005	0.007
	HR at bound ^b	0.771	0.780
	P(Cross) if $HR=1$ ^c	0.005	0.007
	P(Cross) if $HR=0.75$ ^d	0.609	0.650
IA2: 85%* N: 694 Events: 469 Month: 30	Z	2.326	2.230
	p (1-sided) ^a	0.010	0.013
	HR at bound ^b	0.807	0.814
	P(Cross) if $HR=1$ ^c	0.012	0.015
	P(Cross) if $HR=0.75$ ^d	0.794	0.820
Final N: 694 Events: 552 Month: 39	Z	2.138	2.050
	p (1-sided) ^a	0.016	0.020
	HR at bound ^b	0.834	0.840
	P(Cross) if $HR=1$ ^c	0.020	0.025
	P(Cross) if $HR=0.75$ ^d	0.901	0.915
Abbreviations: HR = hazard ratio; IA = interim analysis. The number of events and timings are estimated approximately. *Percentage of the target number of events at final analysis anticipated at interim analysis. ^a p (1-sided) is the nominal α for testing. ^b HR at bound is the approximate HR required to reach an efficacy bound. ^c P (Cross if $HR=1$) is the probability of crossing a bound under the null hypothesis. ^d P (Cross if $HR=0.75$) is the probability of crossing a bound under the alternative hypothesis.			

If the actual number of OS events at the interim and final analyses differs from those specified in the table, the bounds will be updated using this spending function evaluated at the observed information fraction (fraction of observed over expected final events) at each analysis.

The bounds provided in the table above are based on the assumption that the expected number of events at IA1, IA2 and FA are 386, 469 and 552, respectively. At the time of an analysis, the observed number of events may differ substantially from the expected. To avoid overspending at an interim analysis and leave reasonable alpha for the final analysis, the minimum alpha spending strategy will be adopted. At an IA, the information fraction used in Lan-DeMets spending function to determine the alpha spending at the IA will be based on

the minimum of the expected information fraction and the actual information fraction at each analysis. Specifically,

- In the scenario that the events accrue slower than expected and the observed number of events is less than the expected number of events at a given analysis, the information fraction will be calculated as the observed number of events at the interim analysis over the target number of events at FA.
- In the scenario that the events accrue faster than expected and the observed number of events exceeds the expected number of events at a given analysis, then the information fraction will be calculated as the expected number of events at the interim analysis over the target number of events at FA.

The final analysis will use the remaining Type I error that has not been spent at the earlier analyses. The event counts for all analyses will be used to compute correlations.

Of note, while the information fraction used for α spending calculation will be the minimum of the actual information fraction and the expected information fraction, the correlations required for deriving the bounds will still be computed using the actual information fraction based on the observed number of events at each analysis over the target number of events at FA.

The minimum spending approach assumes timing is not based on any observed Z-value and thus the Z test statistics used for testing conditioned on timing are multivariate normal. Given the probabilities derived with the proposed spending method, the correlations based on actual event counts are used to compute bounds that control the Type I error at the specified α level for a given hypothesis conditioned on the interim analysis timing. Since this is true regardless of what is conditioned on, the overall Type I error for a given hypothesis unconditionally is controlled at the specified level. By using more conservative spending early in the study, power can be retained to detect situations where the treatment effect may be delayed.

3.8.5 Safety Analyses

The DMC has responsibility for assessment of overall risk/benefit. When prompted by safety concerns, the DMC can request corresponding efficacy data. DMC review of efficacy data to assess the overall risk/benefit to study participants will not require a multiplicity adjustment typically associated with a planned efficacy interim analysis. However, to account for any multiplicity concerns raised by the DMC review of unplanned efficacy data prompted by safety concerns, a sensitivity analysis for OR, PFS, and OS adopting a conservative multiplicity adjustment will be conducted. For each safety analysis at which an unplanned efficacy analysis is performed, an arbitrary small alpha will be assigned for a nominal bound of 0.00005. Based on this nominal bound, the final bound for OR, PFS, and OS will be adjusted so that final analysis will be controlled within the allocated Type I error.

3.9 SAMPLE SIZE AND POWER CALCULATIONS

The study will randomize 694 participants in a 1:1 ratio into the pembrolizumab + lenvatinib and pembrolizumab + placebo arms, unless a protocol-specified non-binding futility analysis leads to suspension of randomized treatment. PFS and OS are primary endpoints for the study, with ORR as the key secondary endpoint.

Based on the 694 participants with at least 7 months of follow-up, the power of the ORR testing at the allocated $\alpha=0.025$ is approximately 99.6% to detect a 17-percentage point difference between an underlying 30% response rate in the control arm and a 47% response rate in the experimental arm.

For the PFS endpoint, based on a target number of 558 events and 1 efficacy interim analyses at approximately 95% of the target number of events, the study has approximately 95% power to detect an HR of 0.7 at an overall α level of 0.005 (1-sided), and 99% power at an α level of 0.025 (1-sided).

For the OS endpoint, based on a target number of 552 events and 2 efficacy interim analyses at approximately 70% and 85% of the target number of events, the study has approximately 90% power to detect an HR of 0.75 at an overall α level of 0.02 (1-sided), and 91.5% power at an α level of 0.025 (1-sided).

Based on KEYNOTE-052 and KEYNOTE-361 data, the above sample size and power calculations for PFS and OS assume the following:

- PFS follows an exponential distribution with a median of 3.2 months for the control group.
- OS follows an exponential distribution with a median of 10.0 months for the control group.
- Enrollment period of 17 months
- An annual dropout rate of 12% and 5% for PFS and OS, respectively
- A follow-up period of 13 and 22 months for PFS and OS, respectively, after the last participant enrolls.

The sample size and power calculations were performed using R (“gsDesign” package) and EAST 6.4.

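### Do the PFS event counts and follow-up figures in the sSAP need correcting because they do not follow from its own design inputs?

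*SAP*

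**What the plan says.** sSAP Section 3.9 lists the inputs behind the sample size: 694 participants randomised 1:1, exponential PFS with a control median of 3.2 months, a hazard ratio of 0.7, "Enrollment period of 17 months", "An annual dropout rate of 12% and 5% for PFS and OS, respectively", and "A follow-up period of 13 and 22 months for PFS and OS, respectively, after the last participant enrolls". Protocol Section 9.9 repeats these inputs but gives 6 months, not 13, as the PFS follow-up.

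Table 12 (sSAP 3.8.3) gives "N = 694 Events: 530 Month: 24" for the first interim analysis (IA1) and "N = 694 Events: 558 Month: 30" for the final PFS analysis. Its footnote says "The number of events and timings are estimated approximately". The text above the table adds that if the actual number of PFS events "differs from those specified in the table, the bounds will be adjusted". Table 13 (sSAP 3.8.4) gives "N = 694 Events: 386 Month: 24" for the deaths at IA1. In sSAP 3.1 and Table 8 the PFS counts are written as minimums (at least 530, at least 558) next to death counts. Section 3.1 also requires enrolment to be complete.

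The other conflicts are within or between the documents. Futility Analysis 2 (191 PFS events) is labelled 30% in sSAP 3.1 and 34% in Table 9. Minimum follow-up for ORR is 3 months in sSAP 3.8.2 and 7 months in sSAP 3.9.

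**The concern.** A reader who rebuilds the PFS timeline from the Section 3.9 inputs does not get Table 12. The computed counts are clearly higher, and on those inputs the planned PFS total of 558 is passed before IA1. IA1 would then not be a look at 95% of the target. The same calculation does reproduce the OS counts, so the model itself is not obviously at fault.

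In a trial that still had formal tests ahead, this could matter. The interim information fraction sets how much alpha is spent at IA1, and a wrong event projection can put an analysis at the wrong time. Two documents that disagree on follow-up length, and one that labels the same look both 30% and 34%, add to the impression that the design figures were not checked against each other.

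**Working it through.** **1. The plan's own power and boundaries, given 530 and 558 events.** With a Lan-DeMets O'Brien-Fleming spending function at information fraction 530/558 = 0.950:

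| One-sided alpha | Z at 530 / 558 | Stated | Power at HR 0.7 | Stated |
|---|---|---|---|---|
| 0.005 | 2.654 / 2.657 | 2.654 / 2.657 | 94.6% | 94.7% |
| 0.025 | 2.025 / 2.062 | 2.025 / 2.062 | 98.7% | 98.6% |

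These depend on the event counts only, not on when the counts occur. They reproduce.

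**2. Expected PFS events from the Section 3.9 inputs.** Accrual shape is not stated, so assume it is uniform over R = 17 months. Hazards per month:

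- control: ln 2 / 3.2 = 0.2166
- experimental: 0.7 × 0.2166 = 0.1516
- dropout: −ln(0.88)/12 = 0.01065

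For each arm of 347, with event hazard λ, dropout hazard η and s = λ + η:

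E(T) = 347 × (λ/s) × [1 − (e^(−s(T−R)) − e^(−sT))/(sR)]

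| | Control | Experimental | Total | Table 12 |
|---|---|---|---|---|
| Month 24 | 313.7 | 288.9 | 602.5 | 530 (+13.7%) |
| Month 30 | 326.4 | 310.9 | 637.2 | 558 (+14.2%) |

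The model reaches 530 events at month 19.3 and 558 at month 20.7.

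**3. The same formula for OS** (median 10 months, HR 0.75, 5% annual dropout) gives 396.8, 476.5 and 550.7 deaths at months 24, 30 and 39. Table 13 has 386, 469 and 552, so all three agree within 3%.

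**4. Does accrual shape explain the month-30 gap?** Not within 17 months. If everyone enrolled on the last day of month 17, each would have 13 months of follow-up by month 30, and the total would be 313.5 + 284.9 = 598.4.

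**5. How far does this depend on the 17 months?** Table 8 itself puts about 297 participants enrolled at about month 16 and 370 at about month 20. That is 297/16 = 18.6 per month, against 694/17 = 40.8 per month in the design. Take those two counts and assume the other 694 − 370 = 324 enrol between months 20 and 24. Let P(u) be the average event probability after u months, (1/2) Σ (λ/s)(1 − e^(−su)) over the two arms:

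P(4) = 0.508, P(6) = 0.645, P(8) = 0.739, P(10) = 0.802, P(14) = 0.876, P(24) = 0.932, P(30) = 0.940

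Placing each block as late or as early as those counts allow:

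- Month 24, lowest: 297 × 0.739 + 73 × 0.508 + 324 × 0 ≈ 256
- Month 24, highest: 297 × 0.932 + 73 × 0.739 + 324 × 0.508 ≈ 495
- Month 30, lowest: 297 × 0.876 + 73 × 0.802 + 324 × 0.645 ≈ 528
- Month 30, highest: 297 × 0.940 + 73 × 0.876 + 324 × 0.802 ≈ 603

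At the enrolment pace the sSAP itself reports, the month-24 count falls below 530 and the month-30 range contains 558. This pattern does not reproduce both Table 12 counts either, but the direction of the month-24 gap reverses.

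**6. The 95% label.** Against the fixed target, 602.5/558 = 108%. Against the model's own month-30 count, 602.5/637.2 = 94.6%, so the planned spacing of the two looks is kept.

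**7. The smaller figures.**

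- 191/558 = 34.2%, so Table 9 is right and the 30% in Section 3.1 is a slip.
- 30 − 17 = 13, so the sSAP's PFS follow-up fits Table 12 and the protocol's 6 does not.
- 24 − 17 = 7, so the 7-month ORR follow-up fits IA1 and the 3 does not.
- The ORR power calculation does not use follow-up. With 30% against 47%, 347 per arm and one-sided 0.025, the pooled SE is √(2 × 0.385 × 0.615/347) = 0.0369 and the unpooled SE is √((0.21 + 0.2491)/347) = 0.0364. Then (0.17 − 1.96 × 0.0369)/0.0364 = 2.68, which is 99.6%, as stated under both wordings.

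**The case for a change.** The case for correcting the text is that a 14% excess is not rounding when OS agrees within 3%. No accrual pattern inside 17 months gives 558 at month 30. Enrolment that merely finishes by month 24 does not rescue the pair either: any pattern with 530 events at month 24 gives 613 to 615 at month 30 on the stated PFS hazards. The sSAP carries no note, as protocol 9.9 does, that its power section no longer applies, and the edits would be cheap.

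Most of this stands as description. Table 12's PFS counts and timings do not come from the stated inputs, and the three label conflicts are plain. The further step, that the 12% dropout line is the likely culprit, does not stand. A hazard of 0.04 per month gives 535 and 558, and applying 12% as a further flat loss gives 0.88 × 602.5 = 530 and 0.88 × 637.2 = 561. These are fits after the fact, and nothing in the documents supports either. The documents also do not say whether the 12% was meant to cover censoring for new anticancer therapy or missed assessments.

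The missing note in the sSAP does not make its figures live. The sSAP describes itself as a companion to the protocol, and the protocol states that the analyses these figures served will not be done.

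**Conclusion.** No change to the plan follows, because none would gain anything. The gap is about 72 PFS events at month 24 and 79 at month 30, conditional on exponential times, uniform accrual over 17 months and 12% annual dropout. If only the 17-month enrolment is kept, the excess at month 30 is at least 40 events. At the enrolment pace in Table 8 the month-24 count would fall short of 530 instead.

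None of this touches a decision. The PFS counts are minimum triggers, so a higher count still meets them. Table 12 calls its counts and timings approximate, and its boundaries were to be recalculated from actual events. Power and Z values are correct for 530 and 558. The futility boundary was tabulated at 34% and was also to be set from the actual number of events.

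Protocol Section 9 states that the prespecified interim and final analyses will not be performed. Sections 9.8 and 9.9 add that there is no hypothesis testing and that the power calculations do not apply. The estimation methods that protocol Section 9.6.1 retains (Kaplan-Meier curves, stratified Cox hazard ratios and exact intervals for ORR) use no planned event count, information fraction or follow-up assumption. The 30%, the 6 months and the 3 months are clerical slips that a reader can resolve from Table 9 and from the month-24 and month-30 timings.
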